9 STATISTICAL ANALYSIS PLAN

9.1 Statistical Analysis Plan Summary

This section contains a brief summary of the statistical analyses for this trial. Full detail is in the Statistical Analysis Plan (SAP) (Section 9.2).

Statistical Methods

Primary Objective (Safety):

Incidence of adverse experiences will be descriptively summarized. Summary statistics and plots will be generated for the change from baseline values in the vital signs, ECG parameters, and selected laboratory safety parameters for participants, as deemed clinically appropriate. Depending on the safety parameter, the difference from baseline will either be computed on the original scale (raw change from baseline) or on the log scale and back-transformed for reporting (percent change from baseline). Summary statistics for the raw laboratory safety tests, ECGs, and/or vital signs may also be computed, as deemed clinically appropriate.

Primary Objective (Pharmacodynamics):

[REDACTED]

9.2 Responsibility for Analyses

The statistical analysis of the data obtained from this study will be conducted by, or under the direct auspices of, the Early Clinical Development Statistics Department in collaboration with the Quantitative Pharmacology and Pharmacometrics Department and Translational Pharmacology Department of the Sponsor.

If, after the study has begun, changes are made to the statistical analysis plan stated below, then these deviations to the plan will be listed, along with an explanation as to why they occurred, in the Clinical Study Report.

9.3 Hypotheses/Estimation

[REDACTED]

9.4 Analysis Endpoints

Primary Endpoints:

Safety: Primary safety endpoints will include AEs, in addition to laboratory safety tests, ECGs, and VS.

Pharmacodynamics (PD):

The primary PD variables in this study include plasma HIV-1 RNA pre-dose and at the time points listed in the Study Flow Chart up until the time at which ART is initiated.

Secondary Endpoints (PK):

The secondary endpoints in this study include: MK-8558 plasma AUC_{0-last}, AUC_{0-inf}, AUC_{0-168hr}, T_{max}, C_{max}, C_{168hr}, CL/F, V_z/F, and terminal t_{1/2}.

9.5 Analysis Populations

[figure not shown]
All Participants as Treated (APaT): The All Participants as Treated Population consists of all participants who received at least one dose of treatment. This population will be used for assessments of safety and tolerability.

Per-Protocol (PP): The Per-Protocol Population consists of the subset of participants who comply with the protocol sufficiently to ensure that generated data will be likely to exhibit the effects of treatment, according to the underlying scientific model. Compliance covers such considerations as exposure to treatment, availability of measurements and absence of major protocol deviations. Major protocol deviations will be identified to the extent possible by individuals responsible for data collection/compliance, and its analysis and interpretation. Any participants or data values excluded from analysis will be identified, along with their reason for exclusion, in the CSR. At the end of the study, all participants who are compliant with the study procedure as aforementioned and have available data from at least one treatment will be included in the Per-Protocol dataset. This population will be used for the PK and PD analyses.

9.6 Statistical Methods

Primary (Safety):

Incidence of AEs will be descriptively summarized. Summary statistics and plots will be generated for the change from baseline values in the VS, ECG parameters, and selected laboratory safety parameters for participants, as deemed clinically appropriate. Depending on the safety parameter, the difference from baseline will either be computed on the original scale (raw change from baseline) or on the log scale and back-transformed for reporting (percent change from baseline). Summary statistics for the raw laboratory safety tests, ECGs, and/or vital signs may also be computed, as deemed clinically appropriate.

[REDACTED]

Descriptive Statistics:

Individual values will be listed for each PK parameter by treatment, and the following (non-model-based) descriptive statistics will be provided: N (number of participants with non-missing data), arithmetic mean, standard deviation (SD), arithmetic percent coefficient of variation (CV) (calculated as $100 \times \text{standard deviation}/\text{arithmetic mean}$), median, minimum, maximum, geometric mean, and geometric percent CV (calculated as $100 \times \sqrt{\exp(s^2) - 1}$), where s^2 is the observed variance on the natural log-scale).

Exploratory (Pharmacokinetic/Pharmacodynamic):

[REDACTED]

General

For all analyses, data will be examined for departures from the assumptions of the statistical model(s) as appropriate; e.g., heteroscedasticity, nonnormality of the error terms. Distribution-free methods may be used if a serious departure from the assumptions of the models(s) is observed, or suitable data transformations may be applied.

9.7 Interim Analyses

During the in-life portion of the trial, descriptive summary level results (PK, PD/biomarkers and/or safety (labs, vital signs, ECGs)) will be prepared as needed to support decision-making meetings such as dose escalation meetings. The aggregate summaries and individual participant data will be presented for each dose level as appropriate. There are no planned interim analyses to test any formal hypotheses.

9.8 Multiplicity

No multiplicity adjustment is required here since Bayesian method is used.

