Approximately 24 participants will be allocated.

Intervention Groups and Duration:

Intervention Groups	Intervention Group Name	Drug	Dose Strength	Dose Frequency	Route of Administration	Regimen/Treatment Period	Use
	Panel A	MK-8558	400 mg	Once	Oral	Single Dose	Experimental
	Panel B	MK-8558	≤900 mg	Once	Oral	Single Dose	Experimental
	Panel C	MK-8558	≤1600 mg	Once	Oral	Single Dose	Experimental
	Panel D	MK-8558	≤1600 mg	Once	Oral	Single Dose	Experimental
Total Number	24 participants (4 panels of 6 participants each)						
Duration of Participation	Each participant will participate in the study for approximately 9 weeks from the time the participant signs the Informed Consent Form (ICF) through the final contact. After a screening phase of 4 weeks, each participant will receive the assigned intervention (single dose MK-8558). After study drug (MK-8558) administration, each participant will be followed for approximately five weeks.						

Study Governance Committees:

Steering Committee	No
Executive Oversight Committee	No
Data Monitoring Committee	No
Clinical Adjudication Committee	No
Study governance considerations are outlined in Appendix 1.	

Study Accepts Healthy Volunteers: No

A list of abbreviations used in this document can be found in Appendix 11.

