1.2 Schema

The study design is depicted in [Table 1](#).

Table 1 Dosing Scheme for MK-8558

Panel^a	Dose of MK-8558			
A	400 mg			
B ^b		≤900 mg		
C ^b			≤1600 mg	
D ^{b,c}				≤1600 mg with food
a. In each panel, 6 participants will receive a single dose of MK-8558. b. The decision to proceed to the next panel, and the selection of dose will be made following review of data from the preceding panel. c. Optional panel. If the study objectives are met by Panels A-C, Panel D may not be required.				

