4.2.2 Rationale for the Use of Historical Placebo

[figure not shown]
The reduction in viral load for each dose level will be compared to historical placebo data from clinical trials previously conducted by the Sponsor. Evaluation of viral load data from other HIV monotherapy studies has indicated that results are consistent between trials and that on average, participants receiving placebo do not exhibit a change from baseline that differs from the anticipated within-participant variability in viral load. [REDACTED]

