6.3.3 Blinding

This is an open-label study; therefore, the Sponsor, investigator, and participant will know the intervention administered.

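### Does the multiplicity waiver in Section 9.8 break down if the analysis moves to a distribution-free method?

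*Combined protocol and SAP*

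**What the plan says.** Section 9.8 is a single sentence: "No multiplicity adjustment is required here since Bayesian method is used". It gives no other ground.

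The general paragraph that closes Section 9.6 applies across the board: "For all analyses, data will be examined for departures from the assumptions of the statistical model(s) as appropriate". It then offers two remedies: "Distribution-free methods may be used if a serious departure from the assumptions of the models(s) is observed, or suitable data transformations may be applied". No distribution-free method, trigger or order of precedence appears in the visible text.

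The comparisons concerned are those of Section 4.2.2: "The reduction in viral load for each dose level will be compared to historical placebo data from clinical trials previously conducted by the Sponsor". The Synopsis plans "24 participants (4 panels of 6 participants each"), and Table 1 marks Panel D as optional, so there are three or four dose comparisons. Section 6.3.3 makes the trial open-label. Section 9.7 plans no formal interim tests; escalation meetings use descriptive summaries.

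The primary pharmacodynamic method (Sections 9.1 and 9.6), the hypotheses (9.3) and the sample-size text (9.9) are redacted.

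**The concern.** A Bayesian analysis that judges each dose on its own posterior probability is often reported without multiplicity adjustment, and Section 9.8 relies on that alone. Section 9.6 leaves a way out of the Bayesian model once the data have been seen. In the usual sense of the term, a distribution-free method is a rank or permutation test. It produces one p-value per dose, and being Bayesian can no longer be the reason for reading three or four of them unadjusted.

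Two things would be at stake. The chance that some inactive dose is called active might rise in the fallback branch. Also, because panels are small and the people checking assumptions know the dose, the choice of method might decide whether a dose passes.

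**Working it through.** The visible text gives no significance level, posterior threshold or size of the historical placebo group, so there is no figure of the plan's own to reproduce. The check is therefore an illustration.

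**Inputs from the documents:** 6 participants per panel; 3 or 4 panels; each dose compared with historical placebo.

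**Assumed inputs:** 20 historical controls shared by all panels; equal SD; exact one-sided rank-sum test at 0.05; vague-prior posterior probability above 0.95; 'serious departure' read as Shapiro-Wilk p<0.05 on the 24 within-panel residuals.

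**Step 1. Is the fallback more error-prone than the Bayesian rule?** With a vague prior and unknown common variance, the posterior probability exceeds 0.95 exactly when the two-sample t statistic exceeds its 95th percentile on 6 + 20 − 2 = 24 df. So the Bayesian rule has the same per-dose pass rate at the margin, 5%, as an unadjusted one-sided test. Four independent looks at 5% would give 1 − 0.95⁴ = 18.5%. Sharing 6 to 100 controls lowers this to 14.4% to 18.2%.

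Simulated with 20 controls, normal data and a true effect exactly at the tested margin (60,000 trials):

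| Rule | One panel | Any of 3 | Any of 4 |
|---|---|---|---|
| Bayesian | 4.99% | 13.15% | 16.62% |
| Rank-sum | 4.77% | 12.67% | 16.20% |

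The rank-sum branch is slightly lower, because exact rank tests cannot use the whole 5%.

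**Step 2. Does choosing the method after looking at the data add error?** Chance that any of four doses passes at the margin:

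| Data | Bayesian throughout | Switch on Shapiro-Wilk |
|---|---|---|
| Normal | 16.5% | 16.5% |
| t, 3 df | 17.1% | 15.9% |

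A separate run of 8,000 trials gave 16.3% and 16.3% (normal), and 16.5% and 15.8% (t, 3 df). The simulation standard error there is √(0.165 × 0.835 / 8,000) = 0.4 percentage points. The switch does not raise the error.

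**Step 3. How often does the switch change a verdict?** Over all trials, the two methods differ on at least one of four panels in 7.4%, 23.6% and 28.5% of cases (normal data; effect 0, 0.5 and 1 SD above the margin). With t (3 df) data the figures are 12.3%, 41.1% and 34.1%. A verdict changes, however, only if the trigger fires as well. It fires in 4.6% of trials with normal data and 29.0% with t (3 df).

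For normal data, multiplying as if the two events were independent gives 0.046 × 0.074 = 0.3%, 0.046 × 0.236 = 1.1% and 0.046 × 0.285 = 1.3%. Simulating the joint event gives 0.3%, 1.2% and 1.3%, with up to 1.4% in a repeat. For t (3 df) the simulated joint figures are 4.5%, 13.5% and 12.5%. They exceed the simple products (for example 0.290 × 0.123 = 3.6%) because the outliers that fire the trigger also separate the methods.

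**Step 4. What would tightening the rule bring?**

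- Keeping the Bayesian result primary in every case: with t (3 df) data and a dose 1 SD above the margin, one panel passes in about 75% of trials, against 83% with rank-sum.
- Bonferroni over four rank-sum tests: the any-of-4 chance at the margin falls from 16.2% to 4.5%, but the chance that at least one of four doses passes, when all are 1 SD above it, falls from 94.8% to 77.4% (normal data).
- If the fallback were a one-sample signed-rank test against a fixed value, the smallest one-sided p with 6 participants is 2⁻⁶ = 0.0156. That can never reach 0.05/4 = 0.0125.

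**The case for a change.** The best argument for acting is textual and needs no simulation. Section 9.8 gives one reason; Section 9.6 explicitly covers every analysis; a non-Bayesian result would then be reported unadjusted with no stated ground. The visible safety and PK summaries are descriptive, so the clause bears mainly on the primary viral-load comparison. Section 9.2 requires changes to the plan to be listed in the study report, but a switch that Section 9.6 already permits may not count as a change. With 6 per panel, judging non-normality is partly subjective, and with heavy tails the choice can alter a verdict in up to about one trial in seven. One added sentence would close the gap.

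The literal mismatch stands, and so, in part, does the point about Section 9.2. The rest is weaker. The clause is hedged: it applies as appropriate, is optional, and needs a serious departure. Its other remedy, transformation, can stay inside the Bayesian model. Test, level, precedence and the reading of doses are what the redacted method and hypothesis text would be expected to cover. The heavy-tailed cases in which verdicts change are those in which the rank test is the better tool, as step 4 shows. Knowledge of the dose adds little, since assumption checks always use the observed data and open-label dosing is inherent in the design.

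**Conclusion.** No change is called for. The reason given in Section 9.8 does not literally extend to the distribution-free option in Section 9.6, but following the plan as written is not shown to give a wrong or worse result. Under the assumed inputs, the any-dose false-pass chance with the switch equals or falls slightly below that of the Bayesian analysis alone (16.5% against 16.5% with normal data; 15.9% against 17.1% with t, 3 df). Verdict changes are rare with normal data (about 0.3% to 1.4% of trials) and reach about 5% to 14% only where the fallback does its job. Making the Bayesian result primary in all cases, or adjusting the fallback, are fair alternatives, but each costs power in a trial with 6 participants per panel and no formal interim tests.

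The figures rest on a rank-sum fallback, 20 shared individual-level controls, levels of 0.05 and 0.95, and a Shapiro-Wilk trigger, none of which the visible text gives. The abbreviation list includes longitudinal data analysis, so the redacted model may be richer than this two-group comparison. If the redacted text leaves precedence open, analysts can settle it sensibly by reporting both results and reading each dose on its own.

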9.9 Sample Size and Power Calculations

CCI [REDACTED]

10 SUPPORTING DOCUMENTATION AND OPERATIONAL CONSIDERATIONS

10.1 Appendix 1: Regulatory, Ethical, and Study Oversight Considerations

10.1.1 Code of Conduct for Clinical Trials

Merck Sharp and Dohme Corp., a subsidiary of Merck & Co., Inc. (MSD)

Code of Conduct for Interventional Clinical Trials

I. Introduction

A. Purpose

MSD, through its subsidiaries, conducts clinical trials worldwide to evaluate the safety and effectiveness of our products. As such, we are committed to designing, implementing, conducting, analyzing and reporting these trials in compliance with the highest ethical and scientific standards. Protection of participants in clinical trials is the overriding concern in the design of clinical trials. In all cases, MSD clinical trials will be conducted in compliance with local and/or national regulations (eg, International Council for Harmonisation Good Clinical Practice [ICH-GCP]) and in accordance with the ethical principles that have their origin in the Declaration of Helsinki.

B. Scope

Highest ethical and scientific standards shall be endorsed for all clinical interventional investigations sponsored by MSD irrespective of the party (parties) employed for their execution (eg, contract research organizations, collaborative research efforts). This Code is not intended to apply to trials that are observational in nature, or which are retrospective. Further, this Code does not apply to investigator-initiated trials, which are not under the full control of MSD.

II. Scientific Issues

A. Trial Conduct

1. Trial Design

Except for pilot or estimation trials, clinical trial protocols will be hypothesis-driven to assess safety, efficacy, and/or pharmacokinetic or pharmacodynamic indices of MSD or comparator products. Alternatively, MSD may conduct outcomes research trials, trials to assess or validate various endpoint measures, or trials to determine patient preferences, etc.

The design (ie, participant population, duration, statistical power) must be adequate to address the specific purpose of the trial. Participants must meet protocol entry criteria to be enrolled in the trial.

2. Site Selection

MSD selects investigative sites based on medical expertise, access to appropriate participants, adequacy of facilities and staff, previous performance in clinical trials, as well as budgetary considerations. Prior to trial initiation, sites are evaluated by MSD personnel to assess the ability to successfully conduct the trial.

3. Site Monitoring/Scientific Integrity

Investigative trial sites are monitored to assess compliance with the trial protocol and general principles of Good Clinical Practice (GCP). MSD reviews clinical data for accuracy, completeness, and consistency. Data are verified versus source documentation according to standard operating procedures. Per MSD policies and procedures, if fraud, scientific/research misconduct, or serious GCP-noncompliance is suspected, the issues

are investigated. When necessary, the clinical site will be closed, the responsible regulatory authorities and ethics review committees notified.

B. Publication and Authorship

Regardless of trial outcome, MSD commits to publish primary and secondary results of its registered trials of marketed products in which treatment is assigned, according to the prespecified plans for data analysis. To the extent scientifically appropriate, MSD seeks to publish the results of other analyses it conducts that are important to patients, physicians, and payers. Some early phase or pilot trials are intended to be hypothesis-generating rather than hypothesis testing, in such cases, publication of results may not be appropriate since the trial may be underpowered and the analyses complicated by statistical issues such as multiplicity.

MSD's policy on authorship is consistent with the recommendations published by the International Committee of Medical Journal Editors (ICMJE). In summary, authorship should reflect significant contribution to the design and conduct of the trial, performance or interpretation of the analysis, and/or writing of the manuscript. All named authors must be able to defend the trial results and conclusions. MSD funding of a trial will be acknowledged in publications.

III. Participant Protection

A. Ethics Committee Review (Institutional Review Board [IRB]/Independent Ethics Committee [IEC])

All clinical trials will be reviewed and approved by an IRB/IEC before being initiated at each site. Significant changes or revisions to the protocol will be approved by the ethics committee prior to implementation, except changes required urgently to protect participant safety that may be enacted in anticipation of ethics committee approval. For each site, the ethics committee and MSD will approve the participant informed consent form.

B. Safety

The guiding principle in decision-making in clinical trials is that participant welfare is of primary importance. Potential participants will be informed of the risks and benefits of, as well as alternatives to, trial participation. At a minimum, trial designs will take into account the local standard of care.

All participation in MSD clinical trials is voluntary. Participants enter the trial only after informed consent is obtained. Participants may withdraw from an MSD trial at any time, without any influence on their access to, or receipt of, medical care that may otherwise be available to them.

C. Confidentiality

MSD is committed to safeguarding participant confidentiality, to the greatest extent possible. Unless required by law, only the investigator, Sponsor (or representative), ethics committee, and/or regulatory authorities will have access to confidential medical records that might identify the participant by name.

D. Genomic Research

Genomic research will only be conducted in accordance with a protocol and informed consent authorized by an ethics committee.

IV. Financial Considerations

A. Payments to Investigators

Clinical trials are time- and labor-intensive. It is MSD's policy to compensate investigators (or the sponsoring institution) in a fair manner for the work performed in support of MSD trials. MSD does not pay incentives to enroll participants in its trials. However, when enrollment is particularly challenging, additional payments may be made to compensate for the time spent in extra recruiting efforts.

MSD does not pay for participant referrals. However, MSD may compensate referring physicians for time spent on chart review to identify potentially eligible participants.

B. Clinical Research Funding

Informed consent forms will disclose that the trial is sponsored by MSD and that the investigator or sponsoring institution is being paid or provided a grant for performing the trial. However, the local ethics committee may wish to alter the wording of the disclosure statement to be consistent with financial practices at that institution. As noted above, all publications resulting from MSD trials will indicate MSD as a source of funding.

C. Funding for Travel and Other Requests

Funding of travel by investigators and support staff (eg, to scientific meetings, investigator meetings, etc.) will be consistent with local guidelines and practices.

V. Investigator Commitment

Investigators will be expected to review MSD's Code of Conduct as an appendix to the trial protocol, and in signing the protocol, agree to support these ethical and scientific standards.

10.1.2 Financial Disclosure

Financial Disclosure requirements are outlined in the US Food and Drug Administration Regulations, Financial Disclosure by Clinical Investigators (21 CFR Part 54). It is the Sponsor's responsibility to determine, based on these regulations, whether a request for Financial Disclosure information is required. It is the investigator's/subinvestigator's responsibility to comply with any such request.

The investigator/subinvestigator(s) agree, if requested by the Sponsor in accordance with 21 CFR Part 54, to provide his/her financial interests in and/or arrangements with the Sponsor to allow for the submission of complete and accurate certification and disclosure statements. The investigator/subinvestigator(s) further agree to provide this information on a Certification/Disclosure Form, commonly known as a financial disclosure form, provided by the Sponsor. The investigator/subinvestigator(s) also consent to the transmission of this information to the Sponsor in the United States for these purposes. This may involve the transmission of information to countries that do not have laws protecting personal data.

